7.1 Sample Size Determination

The sample size as stated above was derived by a power analysis. A power analysis indicated that a total sample size of 200 patients randomized equally (1:1 randomization) to each treatment arm (i.e trigger finger, De Quervain's disease, and tennis elbow) without any blocking or stratification would provide 80% statistical power (alpha=.05, beta=0.20) to detect a 10% difference in mean DASH scores between cohorts assuming a common standard deviation of 25% (effect size = 10/25 = 0.4). To account for an estimated 30% loss to follow-up, we plan to enroll a total of 260 patients per treatment arm (i.e. trigger finger, De Quervain's disease, and tennis elbow). In total, there will be approximately 780 patients enrolled among all treatment arms, however we expect the trigger finger group to be the treatment arm that most rapidly enrolls patients.

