7.2 Statistical Methods

Statistics will be conducted by the statistician on faculty with the NYU Hospital for Joint Diseases. Primary analysis will consist of comparisons of the baseline functional scores (quickDASH and EQ5D). These scores will be analyzed and compared to subsequent scores at the various follow-ups (4-weeks, 8-weeks,

12-weeks, 6 months). In addition, changes in scores will also be analyzed between the baseline scores and the subsequent follow-ups. Statistical significance will be determined by p-values less than 0.05.

Secondary analysis will consist of physical exam findings and resolution of symptoms following injections as well as grip or pinch strength using pressure dynamometers to gage improved function following injections as well. In addition, observation of side effects will also be included in the secondary analysis.

8 Safety and Adverse Events

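### Section 7.2 plans two overlapping analyses of the same scores, with no precedence, no stated drug contrast and no baseline adjustment; one baseline-adjusted comparison at a named visit would be at least as precise and would give a single primary result

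*Combined protocol and SAP*

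**What the plan says.** The efficacy analysis is in Section 7.2 of the combined protocol and SAP. It starts from the baseline quickDASH and EQ-5D scores and says: "These scores will be analyzed and compared to subsequent scores at the various follow-ups", listing 4, 8 and 12 weeks and 6 months. It then adds that "changes in scores will also be analyzed between the baseline scores and the subsequent follow-ups". The only decision rule is "Statistical significance will be determined by p-values less than 0.05".

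Section 7.2 names no test, model, covariate or primary visit, and no order between the two analyses. It does not say that ketorolac and dexamethasone are compared on these scores. That contrast appears only in Section 7.1, where the trial is sized to "detect a 10% difference in mean DASH scores between cohorts", "assuming a common standard deviation of 25% (effect size = 10/25 = 0.4"), with "80% statistical power (alpha=.05, beta=0.20"). Section 7.1 also rules out blocking and stratification.

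Section 3.4 recognises that pretreatment severity affects prognosis, but applies this only to the decision to stop the study on failure rates.

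**The concern.** Two analyses of the same scores, at four visits and on two instruments, give 2 × 4 × 2 = 16 possible results per disease, and none is designated as the answer. If both are carried out as drug comparisons, they share the follow-up data but treat baseline differently. The score comparison ignores it, and the change comparison subtracts it in full. After a chance baseline imbalance, which simple randomisation leaves uncontrolled, the estimates shift in opposite directions. The choice between them could then be made after the data are seen.

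Efficiency is also at stake. The baseline score is collected from every patient, and using it as a covariate adds precision whenever baseline and follow-up are correlated. Section 7.1 expects 30% loss to follow-up, so that precision is worth having.

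**Working it through.** **Inputs from Section 7.1.** Difference 10, SD 25, alpha 0.05, power 80%, 1:1 allocation, 200 per disease (100 per drug), 260 enrolled, 30% loss.

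**Assumptions.** The test is two-sided. The 25 is the SD of a single score, equal at baseline and follow-up. DASH in 7.1 and quickDASH in 7.2 are on the same scale. The baseline-to-follow-up correlation r is not in the documents, so 0.3, 0.5 and 0.7 are shown.

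**Reproducing the plan.** A two-sample t-test with effect size 10/25 = 0.4 needs 99.08 per drug, so 100 per drug and 200 in total, as stated. A one-sided test would need 78 per drug (156), which does not fit.

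**SD for each analysis.**
- Score: 25.
- Change: 25 × √(2(1 − r)) = 29.6 / 25.0 / 19.4 at r = 0.3 / 0.5 / 0.7.
- Baseline-adjusted: 25 × √(1 − r²) = 23.8 / 21.7 / 17.9.

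The adjusted variance is (1 − r²) times that of the score. It is (1 − r²)/(2(1 − r)) = (1 + r)/2 times that of the change. Neither ratio exceeds 1, so adjustment is never less precise than either, apart from a negligible degree-of-freedom cost.

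**Power at one visit** (two-sided t-test, effect size 10/SD). The 91 per drug is 260 × 0.70 = 182, halved.

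| Analysis | 100 per drug, r = 0.3 / 0.5 / 0.7 | 91 per drug, r = 0.3 / 0.5 / 0.7 |
|---|---|---|
| Score | 80.4% at every r | 76.5% at every r |
| Change | 66.2 / 80.4 / 95.3% | 62.1 / 76.5 / 93.4% |
| Adjusted | 83.9 / 90.1 / 97.6% | 80.3 / 87.3 / 96.4% |

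With 91 per drug, adjusted power is 77.0% at r = 0.1 and 78.2% at r = 0.2. Below about 0.3, adjustment does not restore 80%.

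**How far the two estimates can separate.** The change difference equals the score difference minus the baseline difference. The standard error of the baseline difference is 25 × √(2/100) = 3.54. A one-standard-error imbalance therefore puts the two estimates 3.5 points apart, about a third of the 10-point target.

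**How often the two tests disagree** (one visit, 100 per drug). The test statistics have correlation √((1 − r)/2) = 0.59 / 0.50 / 0.39. With a true 10-point difference, the expected value is 10/3.54 = 2.83 for the score. For the change it is 2.83 × 25/SD of change = 2.39 / 2.83 / 3.65. The bivariate normal then gives disagreement on significance in 26 / 22 / 19% of trials. Simulations of 20,000 trials agree to within about one percentage point. With no effect, at least one test is below 0.05 in about 9% of trials.

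**Across four visits, one score** (5,000 simulated trials, equal correlation between all visits). The chance of at least one false positive is about 26% with both analyses, against 13–17% with the follow-up score alone.

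**The case against.** The strongest reply is that Section 7.2 names no method, so it cannot be said to have chosen a poor one. A reader might infer that the plan commits to unadjusted tests at each visit separately and discards patients who miss a visit. The text does not say that. It lists time points, has no available-case rule, and does not exclude a repeated-measures or adjusted model. Taken literally, it describes within-patient comparisons with baseline. This part of the reply stands, and the figures above are therefore conditional on the drugs being compared on scores and on changes. It does not rescue the plan, because a section that leaves both the drug contrast and the model open still leaves the primary result to be chosen.

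A reader might also infer that the stated 80% power fails. It does not: 100 analysed per drug give 80% on the follow-up score, and the loss is only relative to the adjusted model. The change analysis falls below 80% with 100 per drug only if r is below 0.5 and 25 is the SD of a score. The reference to mean DASH scores in 7.1 favours that reading but does not settle it. If 25 is the SD of change, the change analysis has the stated power.

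Nor do the two analyses necessarily conflict. Under randomisation both estimate the same mean difference, so they can differ, and in most simulated trials they agreed on significance.

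Finally, a reader might infer that a longitudinal model would remove bias from dropout. The documents give no dropout mechanism. Sections 3.4 and 4.4 describe patients leaving for surgery when symptoms do not improve, so it cannot be taken for granted that dropout depends only on scores already observed. No dropout-bias figure is claimed here.

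**Conclusion.** The point holds in a limited form. Section 7.2 sets out two overlapping analyses of quickDASH and EQ-5D at one significance level, with no precedence, no stated drug contrast and no use of baseline as a covariate. Unadjusted comparisons would be valid under randomisation, so this is an avoidable inefficiency and an open choice of primary result.

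If both analyses are run as drug comparisons at one visit, they disagree on significance in about 19–26% of trials with a true 10-point effect, and the chance that at least one is falsely positive is about 9% instead of 5%. Adjustment gains roughly 4 to 17 percentage points of power over the score with 100 per drug (83.9 − 80.4 to 97.6 − 80.4). With 91 per drug it reaches 80% only if r is about 0.3 or more. All these sizes rest on the assumed r and on 25 being the SD of a score. The ordering of precision does not depend on r when the variances are equal.

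**What to change.** Replace the two sentences on scores in Section 7.2 with one primary analysis, along these lines:

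*For each disease, the primary result is the difference between ketorolac and dexamethasone in quickDASH at [one named visit], with its 95% confidence interval. It is estimated from a repeated-measures model with drug, visit, drug-by-visit, baseline score and baseline-by-visit, and the model allows for several treated sites in one patient. The other visits, and EQ-5D by the same model, are secondary. Any analysis of unadjusted change is a sensitivity analysis.*

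The named visit is essential: a drug-by-visit model without one still leaves four contrasts per score. The allowance for several sites is needed because Sections 4.1 and 5.5 let one patient contribute several sites, on the same drug and under separate identifiers.

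Section 7.1 should say whether 25 is the SD of a score or of a change, and to which visit the 10-point difference applies.

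The cost is a rewording of 7.2, a sponsor decision on the primary visit, a short specification of the within-patient clustering, and the clarification in 7.1. No new measurements or patients are needed.

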8.1 Definitions

Adverse Event

An **adverse event** (AE) is any symptom, sign, illness or experience that develops or worsens in severity during the course of the study. Intercurrent illnesses or injuries should be regarded as adverse events. Abnormal results of diagnostic procedures are considered to be adverse events if the abnormality:

- results in study withdrawal
- · is associated with a serious adverse event
- is associated with clinical signs or symptoms
- leads to additional treatment or to further diagnostic tests
- is considered by the investigator to be of clinical significance

Serious Adverse Event

Adverse events are classified as serious or non-serious. A serious adverse event is any AE that is:

- fatal
- life-threatening
- requires or prolongs hospital stay
- · results in persistent or significant disability or incapacity
- a congenital anomaly or birth defect
- an important medical event

Important medical events are those that may not be immediately life threatening, but are clearly of major clinical significance. They may jeopardize the subject, and may require intervention to prevent one of the other serious outcomes noted above. For example, drug overdose or abuse, a seizure that did not result in in-patient hospitalization, or intensive treatment of bronchospasm in an emergency department would typically be considered serious.

Recording of Adverse Events

At each contact with the subject, information will be sought from each subject on adverse events by specific questioning and, as appropriate, by examination. Information on all adverse events should be recorded immediately in the source document, and also in the appropriate adverse event module of the case report form (CRF). All clearly related signs, symptoms, and abnormal diagnostic procedures results should recorded in the source document, though should be grouped under one diagnosis.

All adverse events occurring during the study period must be recorded. The clinical course of each event should be followed until resolution, stabilization, or until it has been determined that the study treatment or participation is not the cause. Serious adverse events that are still ongoing at the end of the study period must be followed up to determine the final outcome. Any serious adverse event that occurs after the study period and is considered to be possibly related to the study treatment or study participation should be recorded and reported immediately.

8.2 Reporting of Serious Adverse Events and Unanticipated Problems

8.2.1 Notifying the IRB

Federal regulations require timely reporting by investigators to their local IRB of unanticipated problems posing risks to subjects or others. The following describes the NYULMC IRB reporting requirements,

though Investigators at participating sites are responsible for meeting the specific requirements of their IRB of record.

Report Promptly, but no later than 5 working days:

Researchers are required to submit reports of the following problems promptly but no later than 5 working days from the time the investigator becomes aware of the event:

- Unanticipated problems including adverse events that are unexpected and related
 - Unexpected: An event is "unexpected" when its specificity and severity are not accurately reflected in the protocol-related documents, such as the IRB-approved research protocol, any applicable investigator brochure, and the current IRB-approved informed consent document and other relevant sources of information, such as product labeling and package inserts.
 - Related to the research procedures: An event is related to the research procedures if in the opinion of the principal investigator or sponsor, the event was more likely than not to be caused by the research procedures.
 - Harmful: either caused harm to subjects or others, or placed them at increased risk

Other Reportable events:

The following events also require prompt reporting to the IRB, though no later than 5 working days:

- **Complaint of a research subject** when the complaint indicates unexpected risks or the complaint cannot be resolved by the research team.
- **Protocol deviations or violations** (includes intentional and accidental/unintentional deviations from the IRB approved protocol) for any of the following situations:
 - one or more participants were placed at increased risk of harm
 - the event has the potential to occur again
 - the deviation was necessary to protect a subject from immediate harm
- Breach of confidentiality
- Incarceration of a participant when the research was not previously approved under Subpart C and the investigator believes it is in the best interest of the subject to remain on the study.
- New Information indicating a change to the risks or potential benefits of the research, in terms of severity or frequency. (e.g. analysis indicates lower-than-expected response rate or a more severe or frequent side effect; Other research finds arm of study has no therapeutic value; FDA labeling change or withdrawal from market)

Reporting Process

The reportable events noted above will be reported to the IRB using the form: "Reportable Event Form" or as a written report of the event (including a description of the event with information regarding its fulfillment of the above criteria, follow-up/resolution and need for revision to consent form and/or other study documentation).

Copies of each report and documentation of IRB notification and receipt will be kept in the Clinical Investigator's study file.

8.3 Unblinding Procedures

Because of the low side-effect profile for this study it will not be necessary to unblind subjects for any particular reason unless they want to be withdrawn from the study and informed of what drug was given to them. If this were to occur the investigator must inform the sponsor-investigator of all subjects whose treatment was unblinded immediately within 24 hours by phone or fax, followed by a written narrative of the event within 48 hours.

8.4 Medical Monitoring

It is the responsibility of the Principal Investigator and Study Regulatory Sponsor to oversee the safety of the study. This safety monitoring will include careful assessment and appropriate reporting of adverse events as noted above. Medical monitoring will include a regular assessment of the number and type of serious adverse events. A full Data and Safety Monitoring Plan is attached.

9 Data Handling and Record Keeping

9.1 Confidentiality and HIPAA

Information about study subjects will be kept confidential and managed according to the requirements of the Health Insurance Portability and Accountability Act of 1996 (HIPAA). In addition to the data security standards noted below, we will also required a signed subject authorization (incorporated into the study consent form) informing the subject of the following:

- What protected health information (PHI) will be collected from subjects in this study
- Who will have access to that information and why
- Who will use or disclose that information
- The rights of a research subject to revoke their authorization for use of their PHI.

In the event that a subject revokes authorization to collect or use PHI, the investigator, by regulation, retains the ability to use all information collected prior to the revocation of subject authorization. For subjects that have revoked authorization to collect or use PHI, attempts should be made to obtain permission to collect at least vital status (i.e. that the subject is alive) at the end of their scheduled study period.

9.2 Source Documents

Source data is all information, original records of clinical findings, observations, or other activities in a clinical trial necessary for the reconstruction and evaluation of the trial. Source data are contained in source documents. Examples of these original documents, and data records include: hospital records, clinical and office charts, laboratory notes, memoranda, subjects' diaries or evaluation checklists, pharmacy dispensing records, recorded data from automated instruments, copies or transcriptions certified after verification as being accurate and complete, microfiches, photographic negatives, microfilm or magnetic media, x-rays, subject files, and records kept at the pharmacy, at the laboratories, and at medico-technical departments involved in the clinical trial.

9.3 Study Records

The study records will collect the primary data collection instrument for the study. All data required by the protocol must be recorded. All missing data must be explained. Study records will be maintained in a secure area accessible to the Principal Investigator and study staff.

9.4 Study Electronic Data

Data will be maintained on a database on a computer which the investigators of this study as well as research assistants have access (however not everyone will see the data due to blinding of the physicians involved in the study). The data will be kept on an NYU research network drive that is password protected. If the data is shared among the investigators it will also be emailed within the NYU email system which is also password protected and encrypted.

All data will be stored for future use. It will take approximately 1-2 years to obtain the number of patients required for the trigger finger arm of the study due to the multitude of patients requiring trigger finger injections in everyday practice. However, it can take longer for the other arms of the study to collect the required amount of patients. The following list explains how this long term data will be handled:

 Data will contain patient names abbreviated with initials of first and last names as well as medical record numbers attached in order to easily obtain more information on the patient in the hospital electronic medical record (EMR)

- Data will be stored indefinitely until it is determined that enough data has been obtained to publish results.
- Data will be kept on an NYU research network drive that the department of hand surgery maintains and is password protected. The resident investigator of this study along with hand department research assistants will have access to the data however any physicians involved in the treatment of these patients will not be able to see the data for blinding purposes.
- Data stored for future use will continue to be maintained in the event a retrospective review of the data is conducted (pending an IRB approval for this as well). At this time it is unknown what this data can also be used for aside from the primary purpose of the study.
- Once the study is complete the results will be shared among physicians. A subject's research
 data will be provided to subjects upon request. Patient will only be told their personal data
 outcomes and the general outcomes of the study as a whole however other patient information
 will be kept from them as per patient confidentiality rules.
- Storage for future use is not optional. This data needs to be stored because it can be used for other research in the future (retrospective reviews, etc).

9.5 Records Retention

Study source information collected in the EPIC system will be maintained according to institutional standards (and a least 6 years) and other study essential documents will be maintained for a minimum of 6 years after completion of the study and analysis of the study data.

10 Study Monitoring, Auditing, and Inspecting

10.1 Study Monitoring

For full details on study data and safety monitoring, see the accompanying Data and Safety Monitoring Plan for this study. The responsibility for gathering the data will rest with the individual investigators/health care providers that are directly treating the patients (either at the NYU HJD hand clinic on 23rd street or in the private office of hand attending). Individuals treating patients will be informed to relay any unanticipated problems/concerns/adverse events to the resident research coordinator ([name]). Data will be consolidated and sent to the resident researcher for further evaluation and for monitoring during the course of each patient's length of treatment.

The resident research coordinator ([name]) will ensure data accuracy by monthly asking how the data was collected and ensuring individuals are following proper protocol. In addition, data accuracy will also be maintained with quick training sessions on the study to be conducted at the study site once every 2 month basis. This will be done by the hand research coordinators/assistants, the resident researchers, or the principal investigators/attending involved. Monitoring work will be reviewed at regular intervals with the study Principal Investigator.

Patients that ultimately drop out of the study will be monitored for the course of their regularly scheduled follow-up appointments until there are discharged from the clinic or the care of the attending orthopaedic hand surgeon.

Primary and secondary efficacy endpoints will be monitored. Either patients will have resolution of their symptoms (primary endpoint) with improvement in hand function to their desired satisfaction or they must undergo surgery (secondary endpoint) for correction due to failure of the local soft tissue injection in relieving their symptoms.

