1.6 Research Risks & Benefits

1.6.1 Risk of Study Drug

All patients will be monitored closely as per the data and safety monitoring plan established for this project for any side-effects that may arise from using these medications for local soft tissue infections. Patients will be checked for common side effects at the time of their follow-up visits. In addition, the patient will be given instructions to contact the private office/HJD hand clinic to report any potential side effects that they may be experiencing.

Risks associated with dexamethasone injections include (9-11, 22-23):

- Pain/discomfort at the site of injection
- Tendon ruptures
- Subcutaneous fat atrophy
- Skin pigmentation changes
- Cartilage damage
- Hyperglycemic responses in diabetic patients

Risks associated with Ketorolac in the literature refer mainly to systemic or intramuscular administration and no risks are noted for local soft tissue injections. Ketorolac has been shown to cause (28-29):

- Pain/discomfort at the site of injection
- Increased risk for bleeding
- Skin rashes
- Pruritis
- Allergic reactions such as face/throat swelling
- Abdominal pain/GI upset
- Gastrointestinal ulcers/GI bleeding
- Renal impairment

Risks associated with lidocaine mainly involve side-effects from systemic administration which include (30,31):

- CNS depression or excitation (light-headedness, nervousness, apprehension, euphoria, confusion, dizziness, drowsiness, tinnitus, blurred vision, vomiting, twitching, convulsions, unconsciousness, respiratory depression and arrest)
- Bradycardia
- Hypotension
- Cardiovascular collapse
- Allergic reactions

Protection against risks

Patients will be injected using sterile technique to avoid any infectious risk with the medication. Patient will be informed that some discomfort will be experienced with needle injection however small gauge needles will be used to minimize the pain felt by the patient. Any patient that experiences an adverse event will be withdrawn from the study and will follow-up with their primary care provider promptly.

Payment for the office visit and any procedures performed will be billed to the insurance company of the patient and the patient is responsible for any copayments needed.

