3.2 Primary Study Endpoints

The primary endpoint will be functional outcome scores at various follow-up time points using the quickDASH and EQ-5D questionnaire as well as a pain visual analog scale. The primary endpoint for the study would be resolution of symptoms or surgical intervention.

Primary endpoints will depend on the diagnosis of the patient. The following details what will be assessed at each follow-up visit after the initial injection:

- 1) Trigger finger group primary endpoint measures include the resolution of objective triggering and resolution of tenderness at the A1 pulley at subsequent follow-up visits. In addition, patients will be graded based on the Quinnell system to monitor for improvement: 0-normal movement of finger; 1-uneven movement; 2-active correctible locking of digit; 3-passively correctible locking; 4-fixed deformity (15). Patients will complete the quickDASH and EQ-5D questionnaires as well as a pain visual analog scale at each follow-up visit (27).
- 2) De Quervain's tenosynovitis group primary endpoint measures will include objective physical exam findings for the resolution of pain/tenderness over the 1st dorsal extensor compartment and the resolution of pain elicited during the Finkelstein test. In addition, patients will complete the quickDASH and EQ-5D questionnaires as well as a pain visual analog scale at each follow-up visit.
- 3) Lateral epicondylitis of the elbow group primary endpoint measures include the resolution of lateral elbow pain/tenderness over the extensor origin and the resolution of pain at the lateral epicondyle with resisted wrist extension during follow-up examinations. Patient grip strength will also be measured in this cohort using a hand dynamometer. Grip strength will be measured at each follow-up and the average of three tests with 20 second rests in between will be recorded. The contralateral side will also be measured for comparison. Lastly, patients will complete the quickDASH and EQ-5D questionnaires as well as a pain visual analog scale at each follow-up visit.

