3.4 Primary Safety Endpoints

Patients will follow-up after the first injection at 4-weeks, 8-weeks, 12-weeks, and 6 months post injection. During follow-up appointments patients in this study will be monitored based on history and physical exam for any side-effects associated with the administration of local soft tissue injections of dexamethasone or ketorolac.

Patients can withdraw from the study at any time if they wish. Patients whose symptoms do not improve and are candidates for surgery can withdraw from the study and have surgery to correct their specific pathology (secondary endpoint). Patients enrolled in the study will be counseled regarding the likelihood of

the injections working and will be given the opportunity for a second injection at 4 weeks from the time of the first injection if no significant symptoms have resolved. Ultimately it will be up to the patient whether they chose another injection or if they want to resort to a surgical intervention.

Patients who receive ketorolac by randomization as the therapeutic option will have an expected failure rate of approximately 30-50% based on clinical experience and literature review that shows the failure rate of dexamethasone (standard of care) on trigger fingers. The study population will be statistically analyzed biannually to determine if there is a significant difference in the rate of failures between the two groups, however a sizeable study population needs to be established before these conclusions can be drawn. If the rate of failure proves to be statistically significant between the ketorolac and dexamethasone group then the study will have to be ethically abandoned. This determination needs to take into consideration the pretreatment symptoms of the patient since patients who begin treatment with a severe trigger finger (quinnell score=4) have a different prognosis compared to patients who begin with a mild trigger finger (quinnell score=1).

4 Subject Selection and Withdrawal

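### Self-reported scores are tied to charged clinic visits and nothing says they continue after drop-out, so the expected 30% loss is likely to depend on outcome, which extra enrolment cannot correct

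*Combined protocol and SAP*

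**What the plan says.** Section 3.2 ties the questionnaires to attendance. For trigger finger it reads "Patients will complete the quickDASH and EQ-5D questionnaires as well as a pain visual analog scale at each follow-up visit", and the other two diagnoses have equivalent wording. Section 3.4 sets the schedule: "Patients will follow-up after the first injection at 4-weeks, 8-weeks, 12-weeks, and 6 months post injection". No section describes collection by post, telephone or e-mail.

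The visits are ordinary office visits. Section 1.6.1 states "Payment for the office visit and any procedures performed will be billed to the insurance company of the patient" and makes the patient responsible for copayments. Section 6 adds that patients are charged for their normal visit, and section 12.3 rules out stipends.

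Sections 3.4 and 4.4 allow patients who do not improve and are surgical candidates to withdraw and have surgery. Section 10.1 covers those who leave: "Patients that ultimately drop out of the study will be monitored for the course of their regularly scheduled follow-up appointments until there are discharged". It does not say whether they still complete questionnaires.

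Section 7.1 deals with loss by numbers alone: "To account for an estimated 30% loss to follow-up, we plan to enroll a total of 260 patients per treatment arm". Section 7.2 names no analysis population and no missing-data method. Section 9.3 requires only that missing data be explained.

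**The concern.** Several features of the plan make it likely that whether a score is observed depends on how the patient is doing. A recovered patient has little reason to pay a copayment for the 12-week and 6-month visits. A patient whose injection has failed may leave for surgery. Once a patient has dropped out, monitoring ends at clinic discharge, which may come before 6 months.

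Extra enrolment protects precision when loss is unrelated to outcome. It does nothing for loss that is related to outcome, because the additional patients are lost in the same way. If failures are lost more often and one drug has more failures, the patients still observed look more alike than those randomised. The objective in section 2 would be met by either an equal or a better result, so a shrunken difference is not a harmless error. If recovered patients are lost more often, both drugs look worse than they are.

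The quickDASH, EQ-5D and pain scale are completed by the patient, so much of this loss could be avoided. Scores not collected at the time cannot be recovered at analysis.

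**Working it through.** **The plan's own figures.** Section 7.1 gives "would provide 80% statistical power (alpha=.05, beta=0.20) to detect a 10% difference in mean DASH scores between cohorts", with a standard deviation of 25 and so an effect size of 0.4. Sidedness is not stated; two-sided reproduces the result.

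- Per drug: 2 × (1.960 + 0.842)² × 25² / 10² = 98.1, so 99, or 198 per diagnosis. The t-test version gives 99.08, so 100, or 200 per diagnosis. The stated 200 reproduces.
- 260 = 200 × 1.3. Loss of 30% from 260 is 78 patients, leaving 182 (91 per drug), with power of 77.0% by the normal approximation. The 60 added patients cover loss up to 60/260 = 23.1%. This shortfall is a separate point. Here it shows that the allowance is purely numerical and assumes loss unrelated to outcome.

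**Illustration of outcome-related loss.** The documents give no reasons for the 30% and no split by drug, so these inputs are assumptions:

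- mean score 15 if resolved and 45 if failed;
- failure rate p of 30% in one arm and 50% in the other. Section 3.4 mentions 30–50%, but as one expected range for ketorolac, drawn from dexamethasone failure in trigger finger. It is not a contrast between drugs;
- a share l_f of failures and a share l_r of resolved patients lost, the same in both arms.

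Observed arm mean = [(1−p)(1−l_r) × 15 + p(1−l_f) × 45] / [(1−p)(1−l_r) + p(1−l_f)].

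Worked example with l_f = 60% and l_r = 10%:

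- p = 0.30: (0.63 × 15 + 0.12 × 45) / 0.75 = 19.80
- p = 0.50: (0.45 × 15 + 0.20 × 45) / 0.65 = 24.23
- Difference 4.43. Loss is 25% and 35%, averaging 30%.

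| Failures lost | Resolved lost | Loss by arm (p = 30%, 50%) | Arm means | Difference | Change |
|---|---|---|---|---|---|
| 0% | 0% | 0%, 0% | 24.00, 30.00 | 6.0 | – |
| 30% | 30% | 30%, 30% | 24.00, 30.00 | 6.0 | 0% |
| 40% | 23.3% | 28.3%, 31.7% | 22.53, 28.17 | 5.6 | −6% |
| 50% | 16.7% | 26.7%, 33.3% | 21.14, 26.25 | 5.1 | −15% |
| 60% | 10% | 25.0%, 35.0% | 19.80, 24.23 | 4.4 | −26% |
| 70% | 5% | 24.5%, 37.5% | 18.58, 22.20 | 3.6 | −40% |
| 15% | 40% | 32.5%, 27.5% | 26.33, 32.59 | 6.25 | +4% |

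Average loss is 30% in every row with loss except the 70%/5% row, where it is 31%. In the last row the difference is nearly kept, but the arm means are too high by 2.3 and 2.6 points.

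If the failure rate is the same in both arms, the formula gives the same mean in both. The observed difference is then zero, as it should be. In this model, bias between drugs needs a true difference in failure as well as outcome-related loss.

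**The case against.** Several stronger readings are tempting, and the documents do not support them.

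- *The loss will depend on outcome.* Section 7.1 gives 30% without reasons. Dependence is an inference from the withdrawal, charging and discharge wording. It is a likely consequence, not a stated one.
- *The comparison is pulled toward equality by a quarter or more.* The two mechanisms oppose each other: loss of failures narrows the difference, and loss of recovered patients slightly widens it. The 26% and 40% reductions need failures to be lost 6 and 14 times as often as resolved patients; moderate ratios give 6% to 15%. Patients and treating physicians are blinded, which limits loss that differs by drug for other reasons.
- *The patient is billed for study visits.* Section 1.6.1 bills the insurer and leaves copayments to the patient, although section 6 does say patients are charged for the normal visit.
- *Non-improvers are invited to leave.* The text says they can. It also offers a second injection, and section 5.1.2 keeps those patients in the study. Surgery is itself a named endpoint, and the record numbers kept under section 9.4 give a partial route to surgery status.
- *Drop-outs are taken off the study schedule.* The appointments in section 10.1 may be the 4-, 8- and 12-week and 6-month visits. The sentence extends monitoring beyond drop-out; what it lacks is any statement about questionnaires. Patients still enrolled remain scheduled to 6 months.

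Two limits also stand. That no other collection route exists rests on the protocol's silence, and the separate Data and Safety Monitoring Plan cited in sections 8.4 and 10.1 is not available here. Remote questionnaires also cannot replace the examination findings that section 3.2 lists among the primary measures.

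What survives is the gap itself: visit-based self-report, an outcome-related way out, no stated collection of scores afterwards, and a remedy that adds only numbers.

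**Conclusion.** The point holds as a cheap improvement to the design. The expected 30% loss is likely to depend on outcome, and enrolling 260 instead of 200 per diagnosis cannot correct that. The direction and size of any bias are uncertain. Under the assumed means and failure rates, a true difference of 6.0 points is observed as anything from 3.6 to about 6.25, with 5.1 to 5.6 under moderate loss patterns. It is unbiased when loss is unrelated to outcome, or when failure rates and loss mechanisms are the same in both arms. None of these inputs comes from the documents as a contrast between drugs, so the figures show what could happen and do not predict it.

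One related contradiction also affects who is lost. Section 1.6.1 withdraws any patient with an adverse event, while section 4.4 says withdrawal is not needed. The two must be reconciled.

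**What to change.** Amend sections 3.2 and 10.1 as follows.

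- Ask every randomised patient for quickDASH, EQ-5D, pain score and surgery or re-injection status at 4, 8 and 12 weeks and 6 months, unless consent to contact is withdrawn. This includes patients who have surgery, are discharged, miss visits or stop study treatment.
- When a visit is missed, use self-completed forms by post or e-mail, or a telephone call by existing staff who are blinded to allocation. The safeguard is needed because sections 5.6 and 5.8 let the hand department research assistant or the resident in charge know the treatment.
- Record the mode of completion and the reason for any missed score.
- Keep examination and grip measures visit-based.

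The cost is a short protocol and consent amendment and some added time for research assistants already in place. The downside is mixed modes of completion for some scores; recording the mode lets the analysis examine it.
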